#### **Interactions with Subgroups**

Summary tables will be produced for the predefined subgroups and interactions between treatment and these subgroups will be investigated, using a Cox proportional hazard model, with pooled study center as a random effect. A separate model will be used for each interaction to determine its significance.

This will also be presented graphically on a tree plot.

### Secondary Efficacy Analyses

#### **Rate of combined vascular events during the 3-month treatment period**

The rate of combined vascular events occurring during the treatment will be analyzed using a Cox proportional hazard model similar to that in the previous section, with the pooled study center as a random effect. A combined vascular event was defined as any of the 4 following events: ischemic stroke, hemorrhagic stroke, myocardial infarction, or death from cardiovascular causes. This will also be presented graphically on a Kaplan-Meier plot.

Each of the 4 vascular events will also be analyzed using the same method and the event rate for each event will be calculated for each treatment group.

#### **Death from any causes**

The rate of overall death for any cause will be analyzed using a Cox proportional hazard model similar to that in the previous section, with the pooled study center as a random effect. The death rate will be calculated for each treatment group.

### Other Efficacy Analyses

#### **Disability measure**

Changes of the modified Rankin Scale (mRS) between the end of study and baseline will be summarized for the two treatment groups among the survivors during the study. The treatment difference will be tested using student t-test.

---

## Neurological impairment

Changes of NIHSS scores between the end of study and baseline will be summarized for the two treatment groups among the survivors during the study. The treatment difference will be tested using student t-test.

## Quality of life

Health related quality of life will be measured using EuroQol EQ-5D scale among the survivors. Treatment differences will be tested using student t-test.

## Time to withdrawal

The time to withdrawal data will be summarized by treatment group, and compared between treatment groups using Kaplan-Meier estimates.

The hazard ratio for the treatment comparison will be derived using a Cox's proportional hazards model, using time to withdrawal as the outcome variable.

This will also be presented graphically on a Kaplan-Meier plot.

In addition, there is potential for differential effects during the early phase of treatment, and thus treatments will also be compared using the Wilcoxon test.

## Safety Analyses

All analyses of safety data will be carried out using the ITT population.

### Extent of Exposure

The extent of exposure will be calculated as the number of days between start of treatment and end of treatment (i.e. treatment stop date – treatment start date + 1), and categorized into months: <1, 1-2, 2-3 months. Exposure will then be summarized by treatment group.

### Adverse Events

Adverse events (AEs) will be coded using the MedDRA coding dictionary (Version 6.0 or a later release) and grouped by system organ class (as detailed in the study protocol). Separate data display listings and summaries will be presented for adverse events that start prior to first dose of study medication (pre-treatment), whilst on study medication (during treatment) and after the last dose of study medication (post-treatment).

Within each treatment group, the number and percentage of subjects experiencing an AE will be summarized by system organ class and preferred term and Fisher's Exact test will be used to compare the number of each grouped AE event between treatment groups. In addition, a separate summary will be provided for AEs experienced by more than 5% of subjects in either of the treatment groups.

### Deaths and Serious Adverse Events

Summary tables and data displays will be provided for serious adverse events (as detailed in the study protocol). In addition, all deaths and serious AE's will be documented in a case narrative format in the clinical study report.

The number of deaths occurring over the treatment period will be summarized and Fisher's Exact test will

---

be used to compare the number of deaths between treatment groups.

*Adverse Events Leading to Discontinuation of Investigational Product and/or Withdrawal from the Study and Other Significant Adverse Events*

Summary tables will be provided of adverse events leading to discontinuation of study drug and/or withdrawal of the subject.

*Pregnancies (as applicable)*

Any pregnancies reported during this study will be summarized in case narratives.

---

**Attachments**

*Appendix 1: Definition of End Points*

Stroke	Sudden symptoms and signs of focal disturbance of cerebral function associated with cerebral circulation disorders. Etiology would be classified based on SSS-TOAST standard.
Ischemic stroke	An acute focal infarction of the brain or retina. Criteria: (1) rapid onset of a new focal neurological deficit with clinical or imaging evidence of infarction and not attributable to a non-ischemic etiology (not associated with brain infection, trauma, tumor, seizure, severe metabolic disease, or degenerative neurological disease); or, (2) rapid worsening of an existing focal neurological deficit that either (a) persists and is not attributable to a non-ischemic etiology (not associated with brain edema, infection, trauma, tumor, seizure, metabolic disease, or degenerative neurological disease) OR (b) is accompanied by evidence of new acute ischemic changes in the brain seen on an imaging study and clearly differentiated from those due to the index ischemic event.
TIA	A neurological deficit of sudden onset, resolving completely, attributed to focal brain or retinal ischemia without evidence of associated acute focal infarction of the brain. Criteria: rapid onset of a focal neurological deficit that is without evidence of acute focal infarction of the brain, and is not attributable to a non-ischemic etiology (brain infection, trauma, tumor, seizure, severe metabolic disease, or degenerative neurological disease)
Symptomatic intracerebral hemorrhage	Any extravascular blood in the brain associated with clinical deterioration, as defined by an increase of 4 points or more in the score on the NIHSS, or that led to death and that was identified as the predominant cause of the neurologic deterioration. Intracerebral hemorrhage is defined as an acute extravasation of blood into the brain parenchyma. Criteria: evidence of hemorrhage in the brain parenchyma demonstrated by head imaging, surgery, or autopsy
Asymptomatic intracerebral hemorrhage	an acute extravasation of blood into the brain parenchyma without clinical deterioration. Criteria: evidence of hemorrhage in the brain parenchyma demonstrated by head imaging, surgery or autopsy
Other symptomatic intracranial hemorrhage	Any extravascular blood within the cranium associated with clinical deterioration, as defined by an increase of 4 points or more in the score on the NIHSS, or that led to death and that was identified as the predominant cause of the neurologic deterioration. Other Intracranial Hemorrhage is defined as an acute extravasation of blood into the subarachnoid space, epidural space, or subdural space with associated symptoms. Criteria: evidence of hemorrhage in the subarachnoid space, epidural space, or subdural space demonstrated by head imaging, surgery, or autopsy

Other Asymptomatic intracranial hemorrhage
	
An acute extravasation of blood into the subarachnoid space, epidural space, or subdural space without associated symptoms. Criteria: evidence of hemorrhage in the subarachnoid space, epidural space, or subdural space demonstrated by head imaging, surgery, or autopsy

Myocardial infarction with coronary revascularization
	
Evidence of myocardial necrosis in a clinical setting consistent with myocardial ischemia, treated with coronary revascularization. Criteria: The diagnosis of MI will be based on an algorithm developed from the Universal Definition of Myocardial Infarction (Circulation 2007 116:2634-2653) that takes into account 5 categories of clinical information from the acute event: rise and/or fall of cardiac biomarkers, ECG abnormalities, clinical setting, imaging evidence, and pathology.

Myocardial infarction without coronary revascularization
	
Evidence of myocardial necrosis in a clinical setting consistent with myocardial ischemia, not treated with coronary revascularization. Criteria: The diagnosis of MI will be based on an algorithm developed from the Universal Definition of Myocardial Infarction (Circulation 2007 116:2634-2653) that takes into account 5 categories of clinical information from the acute event: rise and/or fall of cardiac biomarkers, ECG abnormalities, clinical setting, imaging evidence, and pathology.

Coronary Revascularization without myocardial infarction
	
A procedure to improve coronary blood flow for documented coronary artery disease, but with no documentation of myocardial infarction. Criteria: Documented coronary angioplasty, stenting, or bypass surgery for demonstrated or presumed coronary artery disease


Ischemic vascular death
	
Death due to ischemic stroke, myocardial infarction, sudden cardiac death, arrhythmia, pulmonary embolism, bowel or limb infarction, or any death not readily attributable to a non-ischemic cause

Hemorrhagic Vascular death
	
Death due to intracranial or systemic hemorrhage

## **Summary of amendments of statistical analysis plan**

### **APPENDIX I :**

#### **Protocol changes version 1.0 (Jan 20, 2009) to 1.1 (May. 25, 2009)**

- ✧ Study objectives (page 4): For Group of clopidogrel plus aspirin, duration of combination of aspirin 75 mg/day is changed from first 30 days into first 21 days.
- ✧ Secondary objectives (page 4): subgroup is added as follows: Time to randomization (<12 hours vs.  $\geq$ 12 hours)
- ✧ Sample Size Considerations (page 6): 80% statistical power to detect a relative risk reduction of 22% is changed into 90% power while sample size of 3800 is replaced by 5100.
- ✧ Number of Centers: Up to about 80 sites is added to about 100 sites.

---

## 研究方案概要

**题目:** 比较在 3 个月内使用氯吡格雷, 合并在前 21 天内使用阿司匹林与在 3 个月内单独使用阿司匹林治疗急性非致残性脑血管病 (TIA 或小卒中) 高危人群的安全性及有效性的多中心、随机、双盲、平行对照的临床试验。

**主要研究目的:** 研究方案为在 TIA/小卒中高危人群中, 在 3 个月内联合应用氯吡格雷 (起始剂量 300mg, 之后 75mg/日) 与阿司匹林 (75mg/日) 治疗 21 天, 之后单独应用氯吡格雷 (75mg/日), 对比在 3 个月内单独应用阿司匹林 (75mg/日) 的安全性及有效性。首次给药在症状发生 24 小时之内。主要研究目的是评价上述两组研究方案在降低 TIA 和小卒中高危人群的 3 个月卒中 (任何类型的卒中, 包括缺血性卒中和出血性卒中) 风险的差异。

**研究设计:** 该项研究为多中心、随机、双盲、双模拟临床试验。主要无效假设为在中高危 TIA 和小卒中患者症状出现 24 小时内使用 3 个月氯吡格雷 (起始剂量 300mg) 合并前 21 天使用阿司匹林 (75mg/日) 与单独使用阿司匹林 (75mg/日) 3 个月随访时发生主要终点事件 (缺血性卒中和出血性卒中) 的风险无差异。

**研究人群:**

年龄 $\geq 40$ 岁的中高危卒中风险（随机化时 ABCD2 评分 $\geq 4$ ）的 TIA（局灶性脑或视网膜缺血导致的神经功能障碍，并在 24 小时内完全消失）或急性非致残性缺血性卒中患者（随机化时 NIHSS $\leq 3$  分），且在症状出现的 24 小时内可以应用研究药物。症状开始的时间定义为“最后看起来正常的时间”。

**入组标准:**

- 年龄 $\geq 40$ 岁。
- 急性非致残性缺血性卒中（随机化时 NIHSS $\leq 3$  分），且在症状出现的 24 小时内可以应用研究药物。症状开始的时间定义为“最后看起来正常的时间”
- 具有中高危卒中风险（随机化时 ABCD2 评分 $\geq 4$ ）的 TIA（局灶性脑或视网膜缺血导致的神经功能障碍，并在 24 小时内完全消失）患者，且在症状出现的 24 小时内可以应用研究药物。症状开始的时间定义为“最后看起来正常的时间”。
- 已签署知情同意书

**排除标准:**

- 根据基线头 CT 或 MRI 诊断为出血或其他病理性脑疾患，例如血管畸形、肿瘤、脓肿或其他常见的非缺血性脑疾病（例如多发性硬化）。

- 仅存在单独的感觉症状（如麻木感），单独的视力改变，单独的头晕或眩晕，但基线头 CT 或 MRI 没有急性梗死证据。
- 随机化时 mRS>2 分（发病前的病史评估）。
- 随机化时 NIHSS $\geq$ 4 分。
- 具有明确的抗凝治疗指征（怀疑存在心源性栓塞，如房颤、已知的人工心脏瓣膜、可疑的心内膜炎等）。
- 存在使用氯吡格雷或阿司匹林的禁忌症：
  - 已知过敏史；
  - 严重的肝功能不全或肾功能不全；

备注：严重的肝功能不全是指 ALT 值>2 倍正常上限或 AST 值>2 倍正常上限；严重的肾功能不全是指肌酐值>1.5 倍正常上限。

- 严重的心功能衰竭、哮喘；
- 存在凝血障碍、系统性出血；
- 既往凝血障碍或系统性出血病史；
- 既往血小板减少或中性粒细胞减少病史；
- 既往有药物引起的血液系统疾病或肝功能异常史；
- 白细胞减少( $<2 \times 10^9/l$ )或血小板减少( $<100 \times 10^9/l$ )；
- 随机化前 24 小时内使用过溶栓药物。

- 颅内出血病史
- 预计需要长期服用非研究性抗血小板聚集药物，或影响血小板功能的非甾体类抗炎药物。
- 随机化前十天内使用过肝素或口服抗凝药物。
- 随机化前三个月内有胃肠道出血或大手术。
- 血管成形术或血管外科手术导致的 TIA 或小卒中。
- 计划中的其他外科手术或介入性治疗可能需要终止服用试验药物。
- 血管成形术或血管外科手术导致的 TIA 或小卒中。
- 患有严重非心血管疾病，预期生存时间小于 3 个月的患者。
- 没有采取有效的避孕措施且妊娠试验阳性记录的育龄期女性。
- 正在接受试验性药物或仪器试验的患者。

[figure not shown]

- 随机化:** 随机码列表将在合同研究组织（CRO）集中生成。
- 患者的药物将按照随机码表进行包装。在治疗期间，患者将接受氯吡格雷/阿司匹林组或者阿司匹林组的研究药物治疗，分配到两组的随机概率为 1:1。
- 在研究第 1 天（基线访视）时，研究治疗号将由中心化的互动语音电话系统（Inter-voice Response System, IVRS）分配。在患者进行随机化之前，分中心研究者必须拨打 IVRS，提供患者信息（例如研究号，患者出生日期和姓名缩写，分中心，随机化距症状发生时间）。随后，研究者将获得研究治疗号，并分发给患者相应的第一盒研究用药。
- 主要有效性终点事件:** 3个月内新发任何卒中事件（缺血性卒中或出血性卒中）
- 研究周期:** 每个受试者随机化后完成 90 天随访；整个试验将花 3 年时间完成。
- 预计中心数:** 在全国临床研究网络中筛选 100 余家中心
- 样本量:** 总样本量 5100 例受试者
- 统计分析:** 对于 ITT 数据集中两组治疗方案，都采用了 Kaplan-Meier 方法来估计 3 个月治疗期内的新发首例卒中（包括缺血和出血性卒中）的时间。此外，采用 Cox 比例风险模型计算两种治疗方案间的风险比（HR 值），模型

中设定中心效应为随机效应. 风险比 (HR 值) 将报告 95%可信区间。

### 3 研究流程

#### 1.1 研究设计图

\*在第1天给予阿司匹林的总剂量(75mg-300mg)包括在第1天内任何时间、任何地点(包括在急诊室)给予患者的阿司匹林。

图 1 CHANCE 研究设计图

## 1.2 研究流程图/表

措施	筛选及入组	治疗期			
		第 1 天	第 21±2 天	第 90±7 天 (终点访视)	终点事件 访视
人口统计学特征	X				
mRS	X		X	X	X
NIHSS	X		X	X	X
ABCD  评分 (仅 TIA)	X				
本次发病症状	X				
体格检查	X		X	X	X
既往病史	X				
当前药物治疗	X		X	X	X
头 CT/MRI	X †				
实验室检查 **	X †				X
心电图	X †				X
核实入组/排除标准	X				
签署知情同意书	X				
随机化	X				
头核磁共振	X ***			X ***	X
留血		X ****			
认知评估 (MoCA)		X *****		X	
EQ-5D 量表				X	
给予第 1 次治疗		X			
给予第 2 次治疗			X		
不良事件/严重不良事件			X	X	X
治疗依从性			X	X	X

† 标准评估：基线期费用将不包括在研究中。  
\*\* 包括：血常规（包括白细胞计数、中性粒细胞计数、血红蛋白、血小板计数等）、凝血象、空腹血糖、肝肾功能（包括肌酐，血清转氨酶等）。  
\*\*\* 包括 T1+T2+DWI+FLAIR+T2\*+MRA 序列。仅参与影像学亚组研究的患者需要完成。根据各分中心情况，可以在随机化前完成，也可以在随机化后完成。  
\*\*\*\* 仅参与病因学亚组研究的患者需要留取。在随机化后尽快完成。  
\*\*\*\*\* 在随机化后 48 小时内尽快完成。

## 2 研究背景

### 2.1 中国急性非致残性脑血管事件的疾病负担

中国是世界上脑血管病负担最大的国家，不仅因为其人口基数庞大，而且中国人群更易罹患脑血管疾病；死于脑

血管疾病的患者数量高达死于心血管疾病的 3 倍。

急性非致残性脑血管事件包括：短暂性脑缺血发作（TIA），其症状持续小于 24 小时；以及急性缺血性小卒中，定义为一种 NIHSS $\leq$ 3 的缺血性卒中，它通常是致残性卒中的先兆。缺血性脑血管事件包括缺血性卒中和短暂性脑缺血发作，是主要的脑血管疾病亚型。在中国，估计每年有超过 200 万的新发卒中事件发生，研究显示其中大约有 65% 为脑缺血事件，在这些脑缺血事件中大于 10% 的患者为缺血性小卒中（数据源于急性脑血管事件登记研究，是全国性的，以医院为基础的登记研究，数据尚未发表）。迄今为止在中国还没有关于 TIA 发病率的报道。在美国每年 TIA 的发病率大约为 68/100,000 至 86/100,000，大约每年有 300,000 人被诊断为 TIA。基于美国流行病学调查研究，估计中国每年大约有将近 100 万人被诊断为新发 TIA。令人们更为担心的是，自从 20 世纪末以来，西方国家卒中的发病率和死亡率逐年降低，然而在中国缺血性卒中的发病率与死亡率却逐年增长，并成为国民健康的第一杀手。

对于非致残性脑血管病患者而言，早期卒中或其他血管事件复发是最令人沮丧的医疗情况之一。一些调查研究表明：即使对于那些采用标准阿司匹林治疗的患者而言，TIA 和缺血性小卒中早期（3 个月）发生致残性卒中的风险也远高于预期。虽然受人群和医院设施的差异性限制，仍有研究表明在 TIA 和缺血性小卒中发生 90 天后发生卒中的危险性高达 10%-20%。

## 2.2 急性非致残性脑血管事件的治疗

对于急性非致残性缺血性脑血管事件，很少有确定的，有效的治疗或预防药物。除了阿司匹林外，唯一被认可的药物是静脉注射的组织纤维蛋白溶酶原激活剂（tPA）。然而，tPA 仅针对症状发生在 3 小时内的患者。患者不适合溶栓的最常见原因是症状逐渐改善或症状太轻而不能保证治疗效果，以及到医院的时间超过了可以使用 tPA 的 3 小时时间窗。因此，对于大多数急性非致残性脑血管事件患者而言尚无有效的急性期治疗措施。

血小板聚集是脑缺血的一个重要作用因素，在其它部位的局部缺血也是一样。目前，对于各种不同的病理生理亚型（包括心源性、小血管卒中、大血管卒中等）抗血小板聚集治疗均可在不同程度上降低卒中发生的风险。

## 2.2.1 阿司匹林

目前为止，阿司匹林是唯一经过研究证实有效的用于脑血管事件患者急性期的抗血小板药物，但是其疗效有限，且疗效被轻度增加的颅内出血风险部分抵消。CAST 和 IST 两个研究招募大约 20000 名缺血性卒中患者治疗 2-4 周，使用阿司匹林用于急性期治疗可降低缺血性卒中复发的风险达 30% (绝对的变化为 0.7%)，同时伴有一小部分增加颅内出血的风险 (相对增加 25%，绝对增加 0.2%)。因此，阿司匹林已经成为卒中急性期治疗的标准用药。关于阿司匹林的最佳剂量一直存在激烈的争论，每天使用剂量范围大概在 50-325mg 之间。对于 TIA 患者，阿司匹林也被认为是标准的治疗，氯吡格雷和阿司匹林-双嘧达莫联合制剂也是替代方案，但是尚无试验证实它们可以用于急性期治疗。

## 2.2.2 双嘧达莫

两个临床试验已经证明在预防卒中复发方面双嘧达莫是有效的，这两个试验分别是：ESPRIT和 ESPS-II。试验同时证明双嘧达莫和阿司匹林合用的疗效优于单独使用阿司匹林的疗效。在 ESPRIT 试验中，双嘧达莫与阿司匹林联合应用，结果显示出血的风险没有增加。但目前仍没有评估在卒中或 TIA 的急性期联合应用双嘧达莫/阿司匹林的临床试验（上述两个试验平均入组时间大于 1 个月），所以在发病 1 月内药物的安全性和有效性尚不得而知。

PROFESS 试验没有达到阿司匹林/缓释双嘧达莫对照氯吡格雷预设定的非劣性检验标准，阿司匹林/缓释双嘧达莫联用组和氯吡格雷组在卒中和其他主要血管事件复发上有相似的比率。主要的出血性事件包括：颅内出血在使用阿司匹林/缓释双嘧达莫中更常见，但是绝对风险降低，且被更少的缺血事件部分抵消。在中国，阿司匹林/缓释双嘧达莫尚未得到 SFDA 的批准。因此，在临床实践中，阿司匹林和氯吡格雷合用是对于卒中高危人群或急性期的唯一可能的联用策略。

## 2.2.3 氯吡格雷

氯吡格雷为噻吩吡啶衍生物，通过阻断二磷酸腺苷受体抑制血小板聚集，并不作用于被阿司匹林抑制的血栓素介导途径。CAPRIE 试验中，氯吡格雷 75mg/日使卒中、心肌梗死或血管性死亡的长期风险降低 8.7%，相对于使用阿

司匹林的心血管疾病患者没有增加出血的风险或其它主要的副作用。这个试验没有设计评价氯吡格雷在卒中急性期治疗中的作用，同时没有试验评价 TIA 或小卒中患者中使用氯吡格雷的有效性。

氯吡格雷在血管事件后作为急性期治疗具有潜在临床治疗基础。氯吡格雷起始剂量 300mg 将产生血小板抑制作用，并在 2 小时内达到稳态水平。

## 2.2.4 联合应用氯吡格雷/阿司匹林

已经有几个血管病试验研究了氯吡格雷联合应用阿司匹林的疗效，其中有两个试验包括了卒中或 TIA 患者。尽管这些试验的结果并不支持在卒中和 TIA 后长期应用氯吡格雷，但这些试验并未检验在该人群中氯吡格雷作为急性期治疗的效果，同时这些试验支持在小卒中或 TIA 后使用氯吡格雷可能收益更大，更加安全。

阿司匹林和氯吡格雷具有协同抗血小板聚集作用，在卒中预防中联合使用可能增加收益。阿司匹林和氯吡格雷已联合应用于冠状动脉、颈动脉、及颅内动脉支架术，并具耐受性。同样，来自心脏临床试验、非急性卒中/TIA 试验，以及最重要的 TIA 和小卒中的急性预试验均支持氯吡格雷与阿司匹林联合应用的价值，如下所述。

### 2.2.4.1 心血管临床试验

CURE 试验表明在急性冠脉综合征人群中在服用阿司匹林同时使用氯吡格雷起始剂量 300mg 继而 75mg/日，3 个月随访结束时阿司匹林联用氯吡格雷组可降低卒中、心肌梗死、血管性死亡的风险达 20%，这种疗效在前 10 天内尤为明显。该试验终点事件中心肌梗死和血管性死亡占了较大比例。阿司匹林联用氯吡格雷组重大出血事件的风险略有增加，但致命性出血事件的风险与对照组并无差异。在 CREDO 研究中，对于那些经皮冠脉介入术后使用阿司匹林的患者中，同时使用氯吡格雷使 1 年心血管事件风险降低 27%。早期获益仅在那些在介入操作前 $\geq 6$  小时内接受了起始剂量氯吡格雷的患者中看到，这可能提示在缺血事件发生数小时内服用起始剂量的重要性。在术后 28 天时重大出血风险绝对增加 1%，但这些出血事件多数与临床操作相关，例如搭桥手术。因此，氯吡格雷与阿司匹林联用能减少急性期冠状动脉缺血事件发生率或在经皮冠状动脉介入手术前的缺血事件发生率。

### 2.2.4.2 非急性期中/ TIA 临床试验

MATCH 试验是一项卒中二级预防试验，入组 7599 例患者，主要为欧洲患者。该研究比较阿司匹林联合应用氯吡格雷与单独应用氯吡格雷的疗效差异。入组的大多数患者（79%）为卒中患者而非 TIA 患者。试验总体结果是阴性的，在减少缺血事件方面有 1% 的绝对获益，但被绝对增加的 1% 的重大出血事件风险所抵消。然而，在亚组分析中，那些在确诊卒中或 TIA 后立即接受治疗的患者有获益增加的趋势，在 7 天之内接受治疗的患者相对危险度（RR）降低 17%。CHARISMA 试验随机入组患有血管病的患者，阿司匹林 75-162mg/日治疗组对比氯吡格雷 75mg/日治疗组以及安慰剂组。与 MATCH 试验类似，该试验结果为阴性，减少缺血事件的疗效被少量的严重出血所抵消。但是，同样与 MATCH 试验类似的是，那些在确定临床事件（包括卒中和 TIA）后立即接受治疗的患者更能获益。CHARISMA 试验（数据未发表）入组 4320 例 TIA 或卒中患者，主要研究者 [name] 和 [name]。研究表明，在卒中后 30 天内随机入组的患者中使用氯吡格雷治疗相对危险度降低 26%，而在 30 天之后随机入组的患者其相对危险度降低 17%，这再次表明早期接受治疗的患者更有可能获益。在 30 天之内或之后接受治疗的随机化入组的卒中或 TIA 患者出血风险并无增加。

#### **2.2.4.4 重大出血事件的风险**

尽管非急性卒中或 TIA 的试验表明联合应用氯吡格雷/阿司匹林增加重大出血事件的风险，但在 TIA 或小卒中后急性期内栓塞的风险极高，且与中等或严重卒中相比预期出血风险较低，因此在这种情况下联合应用氯吡格雷/阿司匹林可能更有效，相对更安全。事实上，TIA 或小卒中患者仅有微小梗死灶或无梗死灶，因此其出血风险可能更接近于仅有心脏疾患的患者，而不是那些完全卒中患者（残疾程度满足之前试验入组标准）。例如，在 TOAST 研究中，使用肝素类药物的 NIHSS > 15 的患者严重脑出血的风险为 14%，而那些非严重卒中患者的风险仅为 0.5%。因此，在 TIA 或小卒中患者中联合使用氯吡格雷/阿司匹林的出血风险应相对较低。

### **2.3 结论**

TIA 或小卒中处于一种易被公众和医生忽视的状态。许多研究表明 TIA 和小卒中在短期内发生卒中的风险高于完全性卒中。如果在发病初期对 TIA 和小卒中立即采取有效治疗，那么将显著降低其整体卒中负担。在这种急性病理生理状态中抗血小板治疗可能担当重大角色。然而，还没有大规模的试验对 TIA 或小卒中进行急性期干预的评价。

FASTER 试验和其它在发生 TIA 或小卒中之后联合应用氯吡格雷和阿司匹林的阴性试验均表明在发生 TIA 或小卒中后立即开始氯吡格雷和阿司匹林联合的治疗可能是有益的。因为这些数据来源于规模较小的预试验研究和亚组分析，尚不能作为临床应用的证据。但它们对 TIA 和小卒中后进行强化抗血小板治疗的大规模临床试验提供了强有力的支持。总之，考虑到上述数据以及 TIA 或小卒中患者具有发生血管性事件的高度风险（尤其是在急性期），本研究提议的设计预期能使患者在获得最大获益的同时使出血事件风险最小。

## 3 研究目的

### 3.1 主要研究目的

该临床试验为随机、双盲、多中心研究。研究方案为在 TIA/小卒中高危人群中，在 3 个月内联合应用氯吡格雷（起始剂量 300mg，之后 75mg/日）与阿司匹林（75mg/日）治疗 21 天，之后单独应用氯吡格雷（75mg/日），对比在 3 个月内单独应用阿司匹林（75mg/日）的安全性及有效性。首次给药在症状发生 24 小时之内。主要研究目的是评价上述两组研究方案在降低 TIA 和小卒中高危人群的 3 个月卒中（任何类型的卒中，包括缺血性卒中和出血性卒中）风险的差异。

### 3.2 次要研究目的

3.2.1. 评估次要复合终点事件：由任何类型的卒中、心肌梗死以及血管性死亡组成。

3.2.2. 评估符合研究方案的目标人群的主要终点事件。目标人群包括无明显中断服药的患者（实际服药剂量小于预期总量的 80%）和未重大违反研究方案的患者。

3.2.3. 分别评价联合应用氯吡格雷/阿司匹林组与单独应用阿司匹林组在下列终点事件发生率上的疗效差异：缺血性卒中、出血性卒中、短暂性脑缺血发作、心肌梗死、血管性死亡。

3.2.4. 评价 mRS 的连续性变化和最后一次随访时 mRS 为 0-2 分的患者的比例。

3.2.5. 比较两种治疗方案对下列事件的安全性差异：

◇ 严重或中度出血（GUSTO 定义，见附表）；

◇ 颅内出血；

◇ 总体死亡率；

◇ 不良事件/严重不良事件

- 血栓性血小板减少性紫癜 (TTP)
- 粒细胞减少
- 超敏反应
- 肾衰竭

3.2.6. 比较在不同病因学分型（非颅内大血管疾病对比颅内大血管疾病）中两种治疗方案的有效性和安全性差异。

3.2.7. 比较在不同目标事件（TIA 对比小卒中）中两种治疗方案的有效性和安全性差异。

3.2.8. 对于那些发病前曾服用阿司匹林和/或氯吡格雷的患者，比较两种治疗方案对他们的有效性和安全性差异。

3.2.9. 比较在不同性别和年龄（<65 岁对比≥65 岁）患者中两种治疗方案的有效性和安全性差异。

3.2.10. 在更多的探索性分析中，评价存活者神经功能残损（NIHSS 评分的改变），认知功能（蒙特利尔认知评估（MoCA）），和生活质量（EQ-5D 量表）。

3.2.11. 比较不同随机化时间（小于 12 小时对比大于 12 小时）两种治疗方案的有效性和安全性差异。

3.2.12. 评估有或没有最初头 CT 或 MRI 影像梗死的证据患者的主要终点事件和颅内出血事件的发生率。

## **4 研究设计和管理概述**

### **4.1 研究设计概述**

该随机、双盲多中心临床试验的主要无效假设为在 TIA 和小卒中患者症状出现 24 小时内使用 3 个月氯吡格雷（起始剂量 300mg）合并前 21 天使用阿司匹林（75mg/日）与单独使用阿司匹林（75mg/日）90 天随访时发生主要终点事件（缺血性卒中和出血性卒中）的风险无差异。

中高危 TIA 患者（随机化时 ABCD 评分 ≥4）和急性非致残性缺血性卒中患者（随机化时 NIHSS ≤3 分）必须随机分

组，并在症状出现的 24 小时内给予首剂研究药物。患者将被随机分为两组：

第一组：	随机化第 1 天	氯吡格雷 300mg+阿司匹林 75-300mg（标签公开）
	第 2 天至 21 天	氯吡格雷 75mg/日+阿司匹林 75mg/日
	第 22 天至 3 个月	氯吡格雷 75mg/日+阿司匹林安慰剂
第二组：	第 1 天	氯吡格雷安慰剂+阿司匹林 75-300mg（标签公开）
	第 2 天至 3 个月	氯吡格雷安慰剂+阿司匹林 75mg/日

评估两组患者在 90 天随访中发生的任何新发卒中风险（缺血性卒中和出血性卒中）。

该研究预计在全国 100 家临床研究网络和 CHANCE 研究临床协作单位开展，招募 5100 例受试者，在 35 个月内完成该研究。数据安全监测委员会（DSMB）将定期监督本研究的安全与进展。

## 4.2 研究时间表

建立了 1 个 3 年研究预算与招募计划，主要研究时间节点如下：

### 研究时间表

注册之前-研究开始	9 个月 (2009.01-2009.09)
招募和随访	19 个月 (2009.10- 2011.04)
随访完成	3 个月 (2011.05-2011.07)
数据分析与文章发表	4 个月 (2011.08-2011.11)
总时间	35 个月

\*研究持续时间(每个患者)=3 个月

### **裁决委员会**

临床终点事件（卒中、心肌梗死、死亡、大出血）将由试验之外的专家（神经科专家、心脏病专家）进行复审。

裁决委员会成员资格（包括资格、角色、职责）应在试验开始之前经由裁决委员会和执行委员会认证。

与临床相关事件的神经影像将首先在分中心阅读，在裁定文件中将包括影像报告。在特殊情况下，裁决委员会可能将要求分中心或中心实验室递交原始影像文件。

裁决委员会成员：[name]（香港），[name]（美国），[name]（美国），[name]，[name]，[name]

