### **Adjudication committee**

Clinical outcome events (stroke, MI, death, overt bleedings) will be reviewed by independent experts (neurologists, cardiologists). An adjudication committee charter including membership, role and responsibilities will be approved before the start of the trial by the Adjudication Committee and the Executive Committee.

Neuroimaging associated with clinical events will be read locally and reports will be included in adjudication packets. The adjudication committee may request actual images from sites or from the core lab in special instances.

Members of adjudication committee: [name] (Hong Kong), [name] (USA), [name] (USA), [name], [name], [name].

---

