#### 4.6.3.4 Safety Endpoint

##### 4.6.3.4.1 Primary safety endpoints

- ✧ Incidence of severe bleeding or moderate bleeding (GUSTO definition, see appendix 6), including fatal bleeding and symptomatic intracranial hemorrhage

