#### **Safety Endpoint**

- Rate of moderate and severe bleeding incidence (GUSTO definition), including fatal bleeding and symptomatic intracranial hemorrhage
- Rate of symptomatic and asymptomatic intracranial hemorrhagic events at 3 months
- Rate of total mortality
- Incidence of AEs/SAEs (as described in the protocol) reported by the investigators

Clinical safety will be assessed by a physical examination including neurological evaluation at Day 1, D21 and D90 visits. Adverse events will be collected at each visit after baseline. Supine blood pressure and heart rate will be measured at each visit. No specific laboratory safety tests are required during this study. However, if a laboratory abnormality is clinically relevant or leads to an adverse event report, specific appropriate actions may be required (see Appendix 5, decision charts). An ECG will be performed at the baseline visit (Day 1).

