#### **4.6.3.4 安全性终点事件**

##### **4.6.3.4.1 主要安全性终点事件**

- ◇ 严重出血事件发生率 (GUSTO 定义，见附件 6)，包括致命性出血和症状性颅内出血；

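### The final English and Chinese protocols give the adjudication committee different bleeding remits, so a site following the Chinese text need not send moderate bleeds, part of the analysed safety outcome, for independent review

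*Supplement*

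**What the plan says.** Both current protocol texts set up an independent adjudication committee in section 4.3. The English sentence reads "Clinical outcome events (stroke, MI, death, overt bleedings) will be reviewed by independent experts". The Chinese sentence reads "临床终点事件（卒中、心肌梗死、死亡、大出血）将由试验之外的专家（神经科专家、心脏病专家）进行复审".

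The bleeding outcome is described in four current places:

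- The English primary safety endpoint (4.6.3.4) is "Incidence of severe bleeding or moderate bleeding (GUSTO definition, see appendix 6), including fatal bleeding and symptomatic intracranial hemorrhage".
- The final SAP (Safety Endpoint) has "Rate of moderate and severe bleeding incidence (GUSTO definition), including fatal bleeding and symptomatic intracranial hemorrhage".
- Chinese safety objective 3.2.5 has "严重或中度出血（GUSTO 定义，见附表", severe or moderate bleeding, as does English 3.2.5.
- The Chinese primary safety endpoint (4.6.3.4) has "严重出血事件发生率 (GUSTO 定义，见附件 6", severe bleeding without the moderate grade.

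Appendix 6 of each protocol gives a three-level GUSTO table, and the two tables are not translations of each other. The SAP contains no grading table and does not mention adjudication.

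**The concern.** Bleeding is the main harm to be set against any reduction in stroke, so the bleeding comparison needs the same independent review in every grade that it counts. The trial runs in about 100 centers, all in China, and the Chinese protocol is plausibly the working text at those sites. If the committee sees only what a site regards as major bleeding, the severe part of the outcome is centrally reviewed, while the moderate part may carry the site's own grade. The boundary between the two grades is then also drawn locally, and the table in the Chinese text differs from the one in the English text.

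**Working it through.** No sample size, power or event figure enters this point. The check is a comparison of the current texts.

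| Item | Final English protocol | Final Chinese protocol | Final SAP |
|---|---|---|---|
| Bleeding sent to the committee (4.3) | Overt bleeding, no severity limit | 大出血 (major bleeding), undefined | Not mentioned |
| Safety objective (protocol 3.2.5) | Severe or moderate | Severe or moderate | Severe or moderate |
| Main bleeding endpoint (protocol 4.6.3.4) | Severe or moderate | Severe only | Moderate and severe |
| Moderate grade (Appendix 6) | Transfusion without hemodynamic compromise | Fluid infusion (输液) short of the severe criteria; includes a fall in hemoglobin or hematocrit and certain intraocular bleeds | No table |
| Place of transfusion in the severe grade (Appendix 6) | Only with hemodynamic compromise | Listed under severe, with no mention of hemodynamic compromise | No table |

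**Step 1: is the difference only a matter of translation?** The other three items (stroke, MI, death) match exactly. Overt describes whether bleeding is apparent; 大出血 describes how large it is. In its background section (2.2.4.4) the Chinese protocol uses the close term 重大出血 where the English has major hemorrhage. That supports reading 大出血 as a statement about severity.

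**Step 2: is it a recorded amendment?** No. Protocol version 1.0 in English already had the overt wording. Neither the English nor the Chinese summary of amendments, which run to version 1.3, lists a change to adjudication.

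**Step 3: can the Chinese term be mapped to a grade?** No. Chinese Appendix 6 uses 严重出血, 中等量出血 and 少量出血. 大出血 is not among them, and the text does not say which of them it covers.

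**Step 4: does the analysed outcome reach below severe?** Yes, according to the English endpoint, the SAP and Chinese objective 3.2.5. Chinese 4.6.3.4 is the exception, which sets the Chinese protocol against its own objective.

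**Step 5: what follows?** The remit in the Chinese text does not oblige a site to send a moderate bleed, although the SAP counts that bleed. Someone at the site must also decide which bleeds amount to 大出血, with no definition to apply.

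**Step 6: can the effect be sized?** Write the true difference in risk between the arms as D = D_sev + D_mod. If severe bleeds are all reviewed and local grading captures a fraction s of true moderate bleeds equally in both blinded arms, the observed difference is D_sev + s × D_mod, before any bleeds are over-graded into the outcome. The documents give none of D_sev, D_mod, s or the over-grading rate, so no figure can be put in. Under-capture alone would shrink the moderate contribution on the absolute scale and leave the ratio within moderate bleeds unchanged. Over-grading would act differently.

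**The case against.** The strongest reply has four parts.

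1. The Chinese remit is a list in parentheses after a general term for clinical endpoint events. It contains no word meaning only, so it does not expressly exclude moderate bleeds. This is correct, and the point is accordingly that a site need not send them, not that it may not.
2. The remit is broadly consistent with the Chinese primary safety endpoint, which is severe bleeding alone. That is also true, but it moves the conflict rather than removing it: the SAP, the English endpoint and Chinese objective 3.2.5 still count moderate bleeding.
3. The adjudication charter and the Manual of Procedures, neither of which is shown, may set a wider scope, and all investigators are to be certified in GUSTO and in outcome event adjudication. These could soften the effect in practice. Training is not independent review, however, and the two protocol texts would still disagree.
4. The English text does not fully secure the matter either. In both languages the adjudication packet is described for neurological and cardiac events only (4.5 and 9.4), and neither says who assigns the grade used in the analysis. This stands and bears on the fix.

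A reader might also infer that a transfused bleed without hemodynamic compromise would escape review under the Chinese text. The documents do not support that example. It is moderate in the English table, but the Chinese table lists bleeding that needs transfusion under severe, so it is among the bleeds most likely to be sent.

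**Conclusion.** The inconsistency is real, is present in the latest version of both texts, and is not explained by any listed amendment. Independent review of moderate bleeds is promised in English and is not secured in Chinese, while the SAP analyses moderate and severe bleeding together. Part of the main safety comparison may therefore rest on local grading, against a table that places the severe/moderate boundary differently.

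This rests on two assumptions: that sites work from the Chinese text, and that the unseen charter does not already widen the remit.

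Two stronger conclusions are tempting and are not supported. One is that a site's grade would be final and could not be changed; no passage says who has the last word on the grade. The other is a stated percentage by which the bleeding excess would shrink; the documents supply no rate or accuracy from which to compute one, and any such loss would apply to the moderate share and not to the severe bleeds that are reviewed. The point is worth correcting because the correction is cheap and concerns the main safety outcome, not because a bias of known size has been shown.

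**What to change.** Make three linked changes:

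1. Amend the adjudication committee sentence in Chinese 4.3 to match the English, and state the remit in GUSTO terms in both languages: every reported overt bleed goes to the committee, so that all grades in the analysed outcome are covered.
2. Reconcile Chinese 4.6.3.4 with Chinese 3.2.5, English 4.6.3.4 and the SAP, so that one bleeding endpoint applies.
3. Reconcile the two Appendix 6 tables so that one grading table applies, and have the SAP refer to it.

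Changing the adjudication sentence alone would leave the endpoint and grading conflicts in place. It would also help to add bleeding to the event packet procedure in 4.5 and 9.4 of both texts, since neither now describes a route for it. If the charter already covers this, a cross-reference is enough.

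The cost is a few lines of text and some additional bleeding reports for an existing committee, a workload to which the English protocol is already committed.
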